The **PREDIN RCT** is a randomized double-blind trial with three parallel arms, providing pregnant women with either usual antenatal care, or a daily pill of 20 or 40 µg/day vitamin D₃ (cholecalciferol), in the first trimester of pregnancy.

Recruitment and allocation

The study will be conducted within the antenatal care in Gothenburg. At a routine visit in early pregnancy, women will receive study information orally and in writing. A signed informed consent is needed to be included as participant in the study. According to clinical praxis, interpreters will be present when needed. In addition, study information will be translated into other languages, e.g. English, Somali and Arabic.

Inclusion criteria for screening for the RCT are age 18-45 years and gestational week <15. Exclusion criteria are multifetal pregnancy, known disorder to the metabolism of vitamin D, calcium or phosphate (e.g. adrenal gland disorders, kidney disease), ongoing treatment with vitamin D of ≥10 µg/day and difficulties understanding the study information.

Included women will be screened for risk of vitamin D deficiency, using a validated screening tool (manuscript under review), and they will be invited to complete the study questionnaires and have blood drawn for later analyses. These data will be used for aim 3 and 4.

Women at high risk of vitamin D deficiency, defined as a screening score ≥15 points, will be randomized to one of the three study arms. Blindness towards both subjects and research staff will be ensured in the two groups receiving vitamin D supplementation. For practical reasons, the group receiving usual care will be open label.

Power for sample size

Power is based on the difference in the primary outcome, proportion of vitamin D sufficiency (25OHD >50 nmol/L) at follow up in the third trimester, between the groups receiving 20 or 40 µg vitamin D per day. Assuming that 50% and 90% achieve vitamin D sufficiency in the respective groups, 17 participants per group is needed. Assuming 50% retention rate, 102 women will be included and randomized to one of the three groups using a computer generated randomization list. To reach the target sample size of 102 women, it is estimated that approximately 500 women will need to be screened. This is based on a 20% prevalence of high risk of vitamin D deficiency according to the screening tool.

Data collection

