At screening, data on socio-demographic factors, ethnicity, dietary intake, eye color, sun exposure, and health status (including use of medications) will be collected using questionnaires. Blood will be drawn and banked for later analysis. Women will be followed up in the third trimester of pregnancy, through assessment of dietary intake and blood draw. Compliance and adverse events will be monitored through questions posed by the midwife in the third trimester at the follow-up visit.

Banked blood will be analyzed for 25OHD and other vitamin D metabolites, nutritional biomarkers, inflammation, hormones and gene variants related to vitamin D metabolism.

[figure not shown]

Figure 1. Study design for the PREDIN study

For all women, information on gestational complications, fetal growth and gestational age at birth will be retrieved from medical records via the antenatal care after birth. Retrieved variables for the child will include weight, length, head circumference, vitality signs (Apgar score), gestational duration, and diagnosis of small-for-gestational age, large for gestational age or intrauterine growth restriction. Data for the pregnant woman will include body weight development, hemoglobin, ferritin, plasma glucose, blood pressure delivery mode and

pregnancy complications (e.g. gestational diabetes, gestational hypertension, and preeclampsia). Analyses of genetic variants relating to D vitamin metabolism will also be analysed.

Analyses of serum 25OHD (25OHD3 and 25OHD2) and vitamin D metabolites (e.g. 3-epi-25-Hydroxyvitamin D3, 1,25-dihydroxyvitamin D [1,25(OH)2D]) and vitamin D binding proteins) in maternal blood will be performed by the golden standard method liquid chromatography tandem-mass spectrometry (LC-MS/MS) in a lab accredited by the vitamin D external quality assessment scheme (DEQAS; <http://www.deqas.org>). Analyses of serum from pregnant women will be performed in batch after the last sample collection. Other analyses of blood includes biomarkers of nutrition status (e.g. nutrients, ferritin, hemoglobin, and metabolomics), inflammation (e.g. CRP, interleukines and cytokines) and bone metabolism, hormones (e.g. cortisol, PTH and sex hormones), as well as gene variants related to vitamin D metabolism.

A total amount of 15 mL blood will be drawn at both screening and follow up. Thus, the total amount of blood drawn will be 30 mL.

Statistical analyses

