Mixed models analyses will be used to investigate the change of vitamin D status over time, adjusting for potential confounders. Also, logistic regression will be performed to investigate the odds of ≥ 50 nmol/l and < 50 nmol/l at follow-up. Interactions for BMI, ethnicity and season will be investigated. First the results including all completers will be evaluated (main analysis), thereafter intention-to-treat analysis will be performed including all randomized participants, and lastly per-protocol analysis will be performed including those $> 80\%$ compliant. Differences in dropouts, compliance and missed visits will be compared between the three arms in order to detect potential bias. Logistic regression analysis will be used to assess differences in dichotomous outcomes (such as gestational complications) between treatment arms, and linear regression analysis for continuous outcome data. The study will be registered at <https://clinicaltrials.gov>.

TIME PLAN

[name] has received funding for the study including from the Swedish state under the agreement between the Swedish government and the county councils, the ALF-agreement (ALFGBG-822451 and LFGBG-932690). Ethical approvals was obtained autumn 2021 (Dnr 2021-03871). Recruitment for the PREDIN RCT will start in winter 2021 and is projected to end by winter 2024. Thereafter, analysis of blood samples will be performed, followed by data handling, statistical analyses and reporting.

REFERENCES

1. Bärebring L, et al. Vitamin D Status during Pregnancy in a Multi-Ethnic Population-Representative Swedish Cohort. *Nutrients*. 2016 Oct 22;8(10).
2. Bärebring L, et al. Preeclampsia and Blood Pressure Trajectory during Pregnancy in Relation to Vitamin D Status. *PLoS One*. 2016;11(3):e0152198.
3. Chen YH, et al. Maternal vitamin D deficiency during pregnancy elevates the risks of small for gestational age and low birth weight infants in Chinese population. *The Journal of clinical endocrinology and metabolism*. 2015 Mar 16;jc20144407.
4. Bärebring L, et al. Trajectory of vitamin D status during pregnancy in relation to neonatal birth size and fetal survival: a prospective cohort study. *BMC pregnancy and childbirth*. 2018 Feb 13;18..
5. Qin LL, et al. Does maternal Vitamin D deficiency increase the risk of preterm birth: A meta-analysis of observational studies. *Nutrients*. 2016;8(5).

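### The between-arm linear regression for continuous outcomes states neither an analysis scale nor the screening value as covariate, which costs precision on the exploratory blood markers if followed literally

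*Combined protocol and SAP*

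**What the plan says.** - **Method.** Under Statistical analyses, arms are compared on continuous outcomes by "linear regression analysis for continuous outcome data". The sentence has no transformation, covariate, residual check, or rank or robust alternative. Adjustment for confounders is mentioned only for the mixed model of vitamin D status.
- **Markers.** The Data collection section lists, among the blood analyses, "biomarkers of nutrition status (e.g. nutrients, ferritin, hemoglobin, and metabolomics", and also "inflammation (e.g. CRP, interleukines and cytokines) and bone metabolism, hormones (e.g. cortisol, PTH and sex hormones". No other between-arm method is offered for them.
- **Two blood draws.** The same section says "A total amount of 15 mL blood will be drawn at both screening and follow up". The samples are banked, and serum is to be assayed in batch once collection has ended.
- **Size.** Under Power for sample size: "Assuming that 50% and 90% achieve vitamin D sufficiency in the respective groups, 17 participants per group is needed". Then: "Assuming 50% retention rate, 102 women will be included and randomized to one of the three groups".
- **Main analysis set.** Statistical analyses: "First the results including all completers will be evaluated (main analysis").

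**The concern.** Inflammation markers and some hormones are positive concentrations that often have a long right tail. On the measured scale, an arm difference in such a marker is a difference in arithmetic means. With 17 women per arm, one or two high values can supply much of the variance. A woman's own screening value is usually the best available predictor of her follow-up value, and the sentence does not call on it.

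What is at stake is precision: wider intervals and missed differences on secondary biology, with one unusual sample able to sway a result. Leaving the scale open also lets it be chosen after the data are seen, across many markers, in a trial whose usual-care arm is open label.

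**Working it through.** **Step 1: the number of completers.** The plan gives 50% and 90% sufficiency. It does not state alpha or power, so two-sided 5% and 80% are assumed. The unpooled formula gives

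n = [0.5×0.5 + 0.9×0.1] × (1.960 + 0.842)² / (0.9 − 0.5)² = 0.34 × 7.849 / 0.16 = 16.68, so 17 per group.

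At 50% retention, 17 / 0.5 = 34 per arm, and 3 × 34 = 102. Both stated figures reproduce, taking equal allocation. About 17 completers per arm is therefore the plan's own expectation for its main analysis.

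**Step 2: assumptions.** The documents give no SD, distribution, correlation or expected effect for any marker. Log-normal markers are assumed, with log SD from 0.3 to 1.2, arm ratios of 1.2 to 2, and screening to follow-up correlation of 0.3 to 0.8. Tests are two-sided at 5%.

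**Step 3: power of four versions of the same linear regression.** Simulation, 17 against 17, correlation 0.6:

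| Setting | Raw | Log | Raw + screening value | Log + screening value |
|---|---|---|---|---|
| Log SD 0.5, ratio 1.5 | 58% | 63% | 73% | 80% |
| Log SD 1.0, ratio 2 | 34% | 51% | 45% | 68% |

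Separate runs agree within about 2 points. A hand check of the log columns uses standard error = log SD × √(2/17), multiplied by √(1 − 0.6²) = 0.8 with the covariate:

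- Log SD 0.5: 0.5 × 0.343 = 0.171. ln 1.5 / 0.171 = 0.405 / 0.171 = 2.37. With the covariate, 0.405 / 0.137 = 2.96.
- Log SD 1.0: ln 2 / 0.343 = 0.693 / 0.343 = 2.02. With the covariate, 0.693 / 0.274 = 2.53.

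Against a critical value of about 2.04, these agree with the simulated powers to within about 2 points.

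**Step 4: where the gain comes from.** At log SD 0.5 the log alone adds 63 − 58 = 5 points, the covariate alone adds 73 − 58 = 15, and both add 80 − 58 = 22. At log SD 1.0 the log alone adds 51 − 34 = 17, the covariate alone adds 45 − 34 = 11, and both add 68 − 34 = 34. At moderate skew, most of the gain is the covariate.

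**Step 5: sensitivity.**

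- *Correlation.* The residual variance factor is 1 − r². It is 0.91 at 0.3, so the standard error falls by only about 5%. At log SD 1.0 and a doubling, log-scale power with the covariate is about 52% at correlation 0.3 and 90% at 0.8, against about 51% without it.
- *Skew.* With the ratio set to give 80% power on the log scale (no covariate), raw-scale power is 78% at log SD 0.3, 75% at 0.5, 70% at 0.7, 60% at 1.0 and 52% at 1.2.
- *Effect size.* At a ratio of 1.2, raw against log power is 17% against 19% at log SD 0.5, and 6% against 8% at 1.0. Scale hardly matters there.
- *Influence.* The most extreme value carries on average 37% of an arm's sum of squares on the raw scale at log SD 0.5 and 50% at 1.0, against 27% on the log scale.
- *False positives.* Raw-scale type I error is 4.7% at log SD 0.5 and 3.7% at 1.0: slightly conservative, not inflated.

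**The case against.** **The plan does not choose the measured scale.** A reader might infer that these markers are to be analysed raw. The text does not say so. Regression of a log-transformed marker is still linear regression, so the remedy fits within the existing sentence. This objection stands: the gap is an unstated scale, with raw only as the literal default.

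**The plan does not exclude the screening value.** A reader might infer that baseline is deliberately ignored. The sentence has no covariate list at all, and the documents do not say that every marker will be assayed at both visits. This also stands, and the remedy must be limited to markers that are.

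**The markers are not tied to this sentence by name.** They appear in lists of examples and in none of the four specific aims. The continuous outcomes described most concretely are birth size, gestational duration and blood pressure, and nothing here makes a skewness case for those. Applying the sentence to the markers is an inference, but a reasonable one: they are continuous and no other between-arm method is given.

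**The size is assumed throughout.** Variability, correlation and effect sizes all come from outside the documents, and the gain will differ by marker. That limits how firmly any single figure can be held. It does not remove the reason to use a screening measurement already in hand, or to fix the scale in advance.

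**Conclusion.** The point holds as a minor one. With the only between-arm model for continuous outcomes carrying no scale and no screening covariate, a literal analysis would be less precise than the banked samples allow. Under the assumptions above, moving from raw and unadjusted to log and adjusted raises power from about 58% to 80% in the moderate-skew example and from 34% to 68% in the strong-skew one. The log contributes materially only from a log SD of about 0.7, and the covariate needs a correlation well above 0.3.

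Two stronger readings are not supported. One is that the trial's main conclusions are at risk: the primary outcome is a proportion analysed by logistic regression, 25OHD change has its own mixed model, and the sample size does not depend on these markers. The other is that the analysis would produce false findings: the raw-scale test errs slightly on the conservative side.

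**What to change.** Add to Statistical analyses:

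- Each blood marker assayed at both visits is analysed by linear regression of the follow-up value on arm, with the same marker's screening value as covariate.
- Right-skewed positive concentrations (for example CRP and cytokines, and any other marker judged skewed before unblinding) are natural-log transformed at both visits. Results are reported as geometric mean ratios with 95% confidence intervals.
- One stated rule covers values below the detection limit.

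Because usual care is open label, skewness should be judged on pooled values with arm hidden. Assaying serum in batch after the last sample leaves time to settle this before results exist.

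The cost is wording only, with no new visits or blood draws. The downsides are that effects are read as ratios rather than differences in concentration units, and that the detection-limit rule has to be agreed.
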